Based on expected availability of OB-GYN respondents in a large physician panel, a convenience sampling approach is applied with a target sample size of 380 physicians who collectively are estimated to have removed approximately 820 Levosert IUS across both indications.

Primary endpoint: Expected usage duration of Levosert for both indications, defined as the difference in time between removal (with or without replacement) and insertion of the device.

Secondary endpoints: Number of IUS prescriptions, number of Levosert prescriptions and removals (with or without replacement), distribution of patients by type of contraception, distribution of patients using IUSs who are receiving Levosert, distribution of patients receiving Levosert for heavy menstrual bleeding who show treatment effectiveness by the end of each year, distribution of patients getting Levosert removed by the end of each year, and level of satisfaction with Levosert.

All analyses will be descriptive (total, by country, by indication). Categorical variables will be summarized using counts and percentages. Continuous variables will be summarized using the number of observations (n), mean, standard deviation (SD), median, minimum, and maximum, interquartile ranges (IQR), and 95% confidence intervals (CI), as appropriate.

Ethical and Regulatory Obligations	The study will be approved by an appropriately constituted Ethics Committee in Czech Republic, Poland, Serbia, and Slovakia. Approval is required for the study protocol, any potential protocol amendments, recruitment material (i.e., screener) and participant facing material (i.e., questionnaire) before any Prescriber can be enrolled. All applicable laws and regulations will be followed within the countries in which the survey is performed.
Sponsor	Gedeon Richter
Study Coordinating Centre	Syneos Health

13-02-2023

3 T	ABLE OF CONTENTS	
1 (GENERAL INFORMATION	4
2 8	SYNOPSIS	
3 1	ΓABLE OF CONTENTS	5
	of Tables	
	of Figures	
4 I	LIST OF ABBREVIATIONS	11
5 F	BACKGROUND AND RATIONALE	12
5.1	Background	
5.2	Rationale	
6 (OBJECTIVES	13
6.1	Primary Objective	
6.2	Secondary Objectives	
7 N	METHODOLOGY	13
7.1	Discussion of Study Design	13
7.2	Survey Population	12
8 8	SELECTION OF SURVEY POPULATION	15
8.1	Prescriber Eligibility Criteria	15
8.1	1.1 Inclusion Criteria	15
8.1	1.2 Exclusion Criteria	15
8.2	Randomization	15
8.3	Risk and Benefit	15
8.4	Study Withdrawal, Removal, and Replacement of Prescribers	15
9 I	DATA MANAGEMENT AND QUALITY CONTROL	

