10.3 Data Analysis

All analyses will be descriptive in nature. Categorical variables will be summarized using counts and percentages. Continuous variables will be summarized using the number of observations (n), mean, standard deviation (SD), median, minimum, and maximum, interquartile ranges (IQR), and 95% confidence intervals (CI), as appropriate. In addition, utilization patterns of Levosert will be visualized using plots or similar techniques.

1. Geographical distribution of Prescribers (by country)

- 2. Count and percentage of Prescribers by ranges of their professional time spent on direct patient care
- 3. Count and percentage of Prescribers by duration of their medical practice
- 4. Count and percentage of Prescribers by practice setting
- 5. Count and percentage of Prescribers having prescribed each brand of levonorgestrel IUS
- 6. Count and percentage of Prescribers having experience removing each brand of levonorgestrel (with or without replacement)
- 7. Descriptive statistics on Prescribers' count of IUS prescriptions in the past 10 years
- 8. Descriptive statistics on Prescribers' count of Levosert prescriptions and removals (with or without replacement), by indication
- 9. Descriptive statistics on Prescribers' count of patients they personally manage in a typical month without COVID-19 restrictions
- 10. Descriptive statistics on percentage of Prescribers' patients by type of contraception, by indication
- 11. Descriptive statistics on percentage of Prescribers' patients using IUSs who are receiving Levosert, by indication
- 12. Distribution of Prescriber's patients at the time of Levosert prescription among age categories, by indication
- 13. Count and percentage of Prescribers among categories of duration-of-effectiveness of Levosert for heavy menstrual bleeding
- 14. Percentage of Prescribers' patients getting Levosert removed by the end of each year, by indication
- 15. Descriptive statistics on the total duration of use of Levosert in patients who use Levosert for more than six years, by indication
- 16. Percentage of Prescribers' patients who use Levosert for heavy menstrual bleeding indication who would continue to show treatment effectiveness by the end of each year
- 17. Distribution of Prescribers' patients among reason-for-removal categories, by indication
- 18. Count and percentage of Prescribers by overall level of satisfaction with Levosert in patients who use it for three or more years, by indication

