Appendix 3: HCP Questionnaire

Q1. In a typical month without COVID-19 restrictions, approximately how many patients do you personally manage?

Please consider patients seen both in-person or via virtual/online visit.

Please exclude any patients only seeking prescription refills.

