# of total patients / month	

- **Q2.** Approximately, how many of your patients are **currently using** one of the following types of contraception by indication?
 - ✓ Oral/pill
 - ✓ Intrauterine device (IUD)
 - ✓ Intrauterine system (IUS)
 - ✓ Hormonal ring
 - ✓ Implant
 - ✓ Injection

	Contraception only	Heavy menstrual bleeding (with and without intended contraception)
# of patients currently using any of the above treatment types	#	#

Q3. Considering **all your patients by indication,** approximately what percentage are currently using the different types of contraception listed below?

	Contraception only	Heavy menstrual bleeding (with and without intended contraception)
Oral/pill	%	%
Intrauterine device (IUD)	%	%
Intrauterine system (IUS)	%	%
Hormonal ring	%	%
Implant	%	%
Injection	%	%
Total	100%	100%

Q4. Considering all your patients currently using intrauterine systems (IUSs) by indication, approximately what percentage are using Levosert (levonorgestrel)?

	Contraception only	Heavy menstrual bleeding (with and without intended contraception)
Proportion of patients currently using IUSs who receive Levosert	%	%

Q5. Considering **all** your patients ever having used and/or currently using **Levosert (levonorgestrel)**, what is the age distribution at the time of prescription, by indication?

	Contraception only	Heavy menstrual bleeding (with and without intended contraception)
16-24 years of age	%	%
25-34 years of age	%	%
35-44 years of age	%	%
45-54 years of age	%	%
55+ years of age	%	%
Total	100%	100%

Q6. When using **Levosert (levonorgestrel)** for **heavy menstrual bleeding (with and without intended contraception)**, what is the average time from insertion to achieving treatment effectiveness (defined as significant reduction in menstrual blood loss)?

1	Less than one month	
2	One to less than two months	
3	Two to less than three months	
4	Three to less than four months	
5	Four months or more	

Q7. In your experience, approximately what percentage of patients using **Levosert (levonorgestrel)** for the following indications need to get it **removed (with or without replacement)** by the end of each year (cumulatively since insertion)?

Please note your responses must be cumulative over time (since insertion).

	Contraception only	Heavy menstrual bleeding (with and without intended contraception)
By the end of Year 1	%	%
By the end of Year 2	%	%
By the end of Year 3	%	%
By the end of Year 4	%	%
By the end of Year 5	%	%

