By the end of Year 6	%	%

VALIDATION MESSAGE REQUIRING TRANSLATION:

ERROR: Please note your responses for each column must be cumulative. For example, your response for the end of year 2 must be equal to or greater than your response for the end of year 1, etc.

Q8. For patients who use **Levosert (levonorgestrel)** for **contraception only** for more than six years, for approximately how many years in total do these patients typically use **Levosert (levonorgestrel)**?

Please feel free to provide a fractional number of years.

	# of years	RANGE 7-10
--	------------	------------

Q9. For patients who use **Levosert** (**levonorgestrel**) for **heavy menstrual bleeding** (with and without **intended contraception**) for more than six years, for approximately how many years in total do these patients typically use **Levosert** (**levonorgestrel**)?

Please feel free to provide a fractional number of years.

	# of years	RANGE 7-10
--	------------	------------

13-02-2023

Q10. Among your patients using Levosert (levonorgestrel) for heavy menstrual bleeding (with and without intended contraception), what percentage would continue to show treatment effectiveness by the end of each year (cumulatively since insertion), while continuing to use the same Levosert (levonorgestrel) device.

Please note your responses must be cumulative over time since insertion.

Treatment effectiveness is defined as significant reduction in menstrual blood loss.

		Heavy menstrual bleeding (with and without intended contraception)
1	By the end of Year 1	%
2	By the end of Year 2	%
3	By the end of Year 3	%
4	By the end of Year 4	%
5	By the end of Year 5	%
6	By the end of Year 6	%
7	Beyond 6 years	%

VALIDATION MESSAGE REQUIRING TRANSLATION:

ERROR: Please note your responses for each column must be cumulative. For example, your response for the end of year 2 must be equal to or less than your response for the end of year 1, etc.

Q11. Considering **all** your patients ever having used and/or currently using **Levosert (levonorgestrel)** for the following indications and who had it removed (with or without replacement), approximately what percentage of these patients had **Levosert (levonorgestrel)** removed for each of the following reasons?

	Contraception only	Heavy menstrual bleeding (with and without intended contraception)
Removed per Schedule (IUS Expiry)	%	%
Planning for family	%	%
Side effects	%	%
Lack of effectiveness	%	%
Menopausal	%	%
Other (specify)	%	%
Total	100%	100%

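### Questionnaire Q3's stem, its six-row table totalling 100% and analysis item 10 do not share one denominator

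*Protocol*

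**What the plan says.** The relevant items stand together in Appendix 3 of the protocol. Q2 to Q4 use the same two columns: contraception only, and heavy menstrual bleeding (HMB) with and without intended contraception.

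- **Q1** asks, for a typical month, "approximately how many patients do you personally manage". It takes one figure, not split by indication.
- **Q2** names six types (pill, IUD, IUS, ring, implant, injection) and asks, by indication, for the number "of patients currently using any of the above treatment types".
- **Q3** starts from "all your patients by indication" and asks "approximately what percentage are currently using the different types of contraception listed below". The rows are the same six types, followed by a total of 100% in each column. There is no row for patients using none of them or something else.
- **Q4** states a restricted base in its row label: "Proportion of patients currently using IUSs who receive Levosert".

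Section 10.3, item 10, plans "Descriptive statistics on percentage of Prescribers' patients by type of contraception, by indication". The Synopsis lists the matching secondary endpoint as "distribution of patients by type of contraception" and names no base.

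**The concern.** A percentage needs one denominator, and here three pieces of text point to different ones. The stem names all patients in an indication. The table can hold only patients on one of six methods. The analysis label goes back to the prescribers' patients in general.

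A prescriber with HMB patients on none of the six types has no row for them. That prescriber must either drop them silently from the base or spread them over the listed rows. Two prescribers with identical practices could settle this differently.

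What is at stake is how the method shares are read. A reader of the report would take item 10 at its word, as the fraction of patients on each method, although the entries may be fractions of method users only. A later analysis plan could relabel the output, but it could not establish which base each respondent had in mind.

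**Working it through.** The plan gives no figure for this item, so there is nothing to reproduce. The check is a comparison of bases, followed by a simple identity.

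**Step 1: the base of each item.**

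| Item | Base as written | Split by indication | Residual row |
|---|---|---|---|
| Q1 | patients managed in a typical month | no | not applicable |
| Q2 | current users of the six types | yes | not applicable |
| Q3, stem | all patients | yes | – |
| Q3, table | six types totalling 100% | yes | none |
| Q4 | current IUS users | yes | not applicable |
| Q11 | patients who had the device removed, totalling 100% | yes | yes, an open other category |
| 10.3, item 10 | prescribers' patients | yes | – |

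Q4 states its restriction, and Q11, which also totals 100%, has a residual row. Q3 has neither. In Section 10.3, item 11 limits itself to IUS users, while item 10 has no limit.

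**Step 2: when stem and table agree.** Let u be the proportion of all patients in a column who use any of the six types, and s the share of one method among those users. Then

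- share of all patients = u × s;
- a column that totals 100% over the six rows returns s;
- ratio of s to the all-patient share = 1/u.

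The two agree only when u = 1, that is, when every patient in the column uses exactly one listed type.

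**Step 3: illustration.** The documents give neither u nor s, so the values below are assumptions. Take s = 25% for the IUS row.

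| Assumed u | All-patient share, u × 25% | Factor 1/u |
|---|---|---|
| 100% | 25.0% | 1.00 |
| 90% | 22.5% | 1.11 |
| 70% | 17.5% | 1.43 |
| 50% | 12.5% | 2.00 |

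The factor applies when the entries are shares among listed-type users. It does not describe a respondent who puts the remaining patients into rows arbitrarily.

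**Step 4: can it be repaired afterwards?** The all-patient share needs u by indication, which is the number of listed-type users divided by the number of all patients, both by indication. Q2 gives the numerator. The only patient total is in Q1, which is a monthly figure not split by indication. So u cannot be formed from the data collected.

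**Step 5: what depends on Q3.** The primary endpoint (Section 10.1) uses the likelihood of removal by year and the duration beyond Year 6, which come from Q7 to Q9. The sample size (Section 10.2, Appendix 1) uses sales, retention and panel figures. Q4 asks for the Levosert share among IUS users directly. None of these uses Q3.

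**The case against.** The strongest reply is that Q2 to Q4 form a funnel. Q2 counts users of six types, Q3 splits the same six types in the same order, and Q4 narrows to IUS users. On that reading, patients by indication means patients using a method for that indication. A 100% split is then right, and a distribution over types sums to 100% by construction. The Synopsis endpoint names no base that this would contradict. This stands: the shares may be exactly what the sponsor wanted. The Q3 stem and the item 10 label nevertheless say something else, and a respondent may follow the stem.

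Three stronger readings are tempting, but the documents do not support them.

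- A reader might infer that every method share will be overstated. That holds only if all patients is the intended base and u is below 1. Neither is established, and the factors above rest on assumed values.
- A reader might infer that the distortion is larger for HMB, because that column includes women without intended contraception. The documents give no usage proportions for either column, so neither a difference nor its direction is shown.
- A reader might infer that the survey software will reject any other total. Q7 and Q10 print a validation message and Q3 does not. The 100% requirement is inferred from the printed total row, although that is its natural meaning.

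**Conclusion.** The point holds as a mismatch of denominators, not as a demonstrated bias. If the intended base is listed-type users, the numbers need no adjustment, but the stem and the item 10 label must change. If it is all patients, the table cannot record the answer and the data collected cannot correct it. In both cases the wording as fixed lets respondents apply different bases.

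The size is unknown, since it depends on u; the factor of 1.1 to 2.0 is an illustration for u between 90% and 50%. The reach is one secondary descriptive endpoint. The severity is low.

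**What to change.** Choose one base and use it throughout. Either change would do:

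1. **Listed-type users.** Begin Q3 with: *Considering the patients you counted in Q2 (current users of any listed type), by indication*. Label item 10 *percentage of current users of the listed types*.
2. **All patients.** Keep the stem and the item 10 label, and add *None* and *Other* rows inside the 100% total.

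The first is the smaller change and fits the order of Q2 to Q4.

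The cost is low but not nil. The questionnaire is fielded in four languages (Section 7.2), so the change must be translated. If it is made after approval, Section 11.2 requires ethics committee review in each country. Section 12.2 exempts purely administrative changes, including inconsistencies, from prior approval. That might cover rewording the stem; new response rows fit it less easily. Sample size, the primary analysis and the other items stay as they are.

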7 METHODOLOGY

This is a retrospective cross-sectional study collecting secondary data on the experience of OB-GYNs who prescribe Levosert in four (4) European countries: Czech Republic, Poland, Serbia, and Slovakia.

Respondents are healthcare providers (HCPs) who have their primary specialization in obstetrics and gynaecology. Hereinafter, this document shall refer to the respondents, who are prescribers of Levosert, as Prescribers. Refer to Section 8.1 for Prescriber eligibility criteria.

The survey will be fielded through an online survey platform tool and data will be stored in a cloud-based environment. The questionnaire will collect quantitative data by means of closed-ended questions.

Prescribers will be asked to report their real-world experience with Levosert in patients who have used or are still using the drug for contraception and HMB (with and without intended contraception). Prescribers will be asked to report about all the patients they have managed with Levosert (including numbers of Levosert prescriptions and replacements or removals). Individual patient data will not be reported. Instead, data will be considered aggregate and will be fully anonymous.

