10.1 Primary Endpoint Definition

The primary objective of this study is to describe the expected real-world usage duration of Levosert for its different indications.

Duration of Levosert usage is defined as the difference in time between removal (with or without replacement) and insertion of the device. In the absence of detailed patient-level data and in the context of this survey, expected duration of Levosert usage for each indication will be calculated as follows:

Expected usage duration of Levosert (years)

$$= \sum_{i=1}^{6} (i \ x \ likelihood \ of \ Levosert \ removal \ in \ Year \ i)$$

+ (likelihood of Levosert removal beyond Year 6 x total expected usage duration in those patients)

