Appendix 1: Supporting Data for HCP Sample Size Determination

A feasibility assessment was conducted to understand the estimated number of Levosert removals since product launch in each country, the total number of practicing OB-GYNs, and the expected number of OB-GYNs that could be recruited from a large physician panel across the study countries (i.e., OB-GYNs who would be eligible and willing to participate).

The number of Levosert removals in the countries of interest has been estimated from:

- 1. The number of pharmacy-level Levosert sales per country and per year from product launch in 2014 until the last full year of product sales which is 2020 (IMS pharmacy sales database, 2021).
- 2. LNG-IUS user retention after 1 to 5 years of usage as reported by a post-marketing study: 0.94, 0.87, 0.82, 0.76, 0.65, respectively (Backman et al., 2001). For years outside the reported years, 0% retention is assumed resulting in a conservative estimate.

Table 2. Levosert Removals Sin	ce Proc	luct Lau	nch, Es	stimatio	n
Country	2020	2019	2018	2017	- 2

	Country	2020	2019	2018	2017	2016	2015	2014	Total
Czech	Sold	5,803	5,320	5,206	4,233	4,326	2,768	99	27,755
Republic	Removed since (estimated)	348	692	937	1,016	1,514	2,768	99	7,374
	Sold	8,736	11,765	8,971	9,282	8,619	7,931	40	55,344
Poland	Removed since (estimated)	524	1,529	1,615	2,228	3,017	7,931	40	16,884
	Sold	690	907	805	794	907	323	0	4,426
Serbia	Removed since (estimated)	41	118	145	191	317	323	0	1,135
	Sold	1,771	1,824	1,733	1,469	1,485	549	3	8,834
Slovakia	Removed since (estimated)	106	237	312	353	520	549	3	2,080
τ	Jser retention (estimated)	94%1	87%²	82%2	76%²	65%²	0%	0%	

The number of practicing OB-GYNs per country has been estimated based on data from multiple sources (WHO 2021, LKCR 2022, NIL 2021)

Distribution by indications has been estimated based on a multinational LNG-IUS patient survey, which showed that 55% of removals were in patients where IUS was prescribed for heavy menstrual bleeding and the remaining 45% for contraception (Römer et al., 2009).

A summary of Levosert sales and removals from product launch until 2020 in the four study countries, the geographical distribution of OB-GYNs, the expected achievable sample of OB-

-

¹ Based on epidemiological survey of 23,885 LNG-IUS users (Backman et al., 2001).

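### Q7 asks for cumulative removal to Year 6 without a follow-up condition or an opt-out, so the primary duration estimate may mix whole-caseload tallies with projected risks

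*Protocol*

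**What the plan says.** Section 10.1 of the protocol computes expected duration as a sum of six yearly terms (year number times likelihood of removal in that year) plus one last term: "likelihood of Levosert removal beyond Year 6 x total expected usage duration in those patients". The yearly likelihoods come from Q7 in Appendix 3, and the duration in the last term comes from Q8 and Q9, which accept only 7 to 10 years.

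Q7 opens "In your experience, approximately what percentage of patients using" Levosert need to have it removed. It has six cumulative rows counted from insertion, the last being "By the end of Year 6". It gives no minimum time since insertion for any row and no way to say that experience is insufficient. Q12, on satisfaction, does offer that option.

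Section 7 describes the scope of the survey: "Prescribers will be asked to report about all the patients they have managed with Levosert", and it covers experience "in patients who have used or are still using the drug for contraception and HMB".

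**The concern.** A cumulative six-year removal percentage means what the formula needs only if the patients in the denominator have had six years in which to be removed. If recent insertions are counted, a device placed two years ago and still in use lowers the reported Year 6 percentage. The formula has no place for such a device except the last term, where it receives at least seven years. The error runs towards longer use, in a study undertaken because data to support a longer duration of use in heavy menstrual bleeding are lacking (Section 5.2).

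Later analysis cannot repair this. The questionnaire collects no insertion dates and no numbers at risk by year, and Section 9.1 rules out patient-level data. Eligibility requires two prescriptions and one removal for heavy menstrual bleeding (Section 8.1.1), so a Prescriber with no six-year patient can qualify and is still shown the Year 6 row.

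**Working it through.** **Inputs from the document.** Sales by year, four countries added from Table 2: 2014: 142; 2015: 11,571; 2016: 15,337; 2017: 15,778; 2018: 16,715; 2019: 19,816; 2020: 17,000; total 96,359. Retention at Years 1 to 5: 0.94, 0.87, 0.82, 0.76, 0.65 (Appendix 1).

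**Assumptions.** Sales year stands for insertion year, with insertions spread evenly within it. Fielding is at 2023.25 (the protocol is dated 13-02-2023). Year 6 retention, S6, is not given and is varied from 0.20 to 0.55. Sales in 2021-22 are not given; they are either left out or set at the 2020 level.

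**Step 1: the plan's own figure.** The Table 2 removals add to 7,374 + 16,884 + 1,135 + 2,080 = 27,473 of 96,359 (28.5%). This agrees with the 27,500 of 96,300 (29%) in Table 3.

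**Step 2: share able to reach six years.**
- By end 2022: (142 + 11,571 + 15,337) / 96,359 = 27,050 / 96,359 = 28.1%.
- By 2023.25, adding a quarter of 2017 sales: (27,050 + 3,944.5) / 96,359 = 32.2%.
- If all 2017 sales are counted (fielding as late as end 2023): 42,828 / 96,359 = 44.4%.

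**Step 3: the formula in short form.** With c1 to c6 the cumulative removals and L the tail answer, Section 10.1 equals 6 - (c1 + c2 + c3 + c4 + c5) + (L - 6)(1 - c6). At L = 7 the last part is simply 1 - c6.

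**Step 4: complete follow-up.** c1 to c5 are 0.06, 0.13, 0.18, 0.24, 0.35, which sum to 0.96. The result at L = 7 is 5.04 + S6.

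**Step 5: whole-caseload tally.** Each cohort contributes only the removals it has had time to show, with retention interpolated linearly.
- Sales to 2020 only: c1 to c5 are 0.060, 0.130, 0.178, 0.224, 0.287 (sum 0.879). At S6 = 0.40, c6 = 0.388, giving 6 - 0.879 + 0.612 = 5.73, against 5.04 + 0.40 = 5.44.
- With 2021-22 sales: c1 to c5 are 0.058, 0.116, 0.152, 0.186, 0.233 (sum 0.745). At S6 = 0.40, c6 = 0.307, giving 6 - 0.745 + 0.693 = 5.95.

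| S6 (assumed) | Year 6 removal, complete | Year 6 removal, tally (without / with 2021-22 sales) | Duration at L = 7, complete | Duration at L = 7, tally | Excess, years |
|---|---|---|---|---|---|
| 0.20 | 0.80 | 0.47 / 0.37 | 5.24 | 5.65 / 5.89 | 0.41 / 0.65 |
| 0.40 | 0.60 | 0.39 / 0.31 | 5.44 | 5.73 / 5.95 | 0.29 / 0.51 |
| 0.55 | 0.45 | 0.33 / 0.26 | 5.59 | 5.79 / 5.99 | 0.20 / 0.40 |

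**Step 6: other summaries on the same model.** At L = 10 the excess is about 0.6-1.4 years, or 1.0-1.9 with 2021-22 sales. The six-year restricted mean, 6 - (c1 + ... + c5), is 5.12 or 5.26 by tally against 5.04, so its excess is about 0.1 or 0.2 years.

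**The case against.** The strongest objection is that Q7 need not be read as a tally. It is in the present tense, asks about the respondent's experience, and counts time from insertion. Where the questionnaire wants a count over every patient ever treated, it says so, as in Q5 and Q11; Q7 does not. The screener's closing text asks for expert opinion as well as experience, and Section 10.1 speaks of expected duration and likelihood. A projected six-year risk is therefore a natural answer, and it does not carry this bias. This stands: it makes the bias conditional, but it does not tell respondents which of the two to give.

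Three stronger readings are tempting and are not supported.
- A reader might infer that respondents are instructed to use their whole caseload. The all-patients wording is in the protocol body, and neither the screener nor the questionnaire repeats it for Q7.
- A reader might infer that the formula counts every device still in place as lasting at least seven years. It acts on reported percentages, so this happens only under the tally reading.
- A reader might infer a contradiction between the definition, "Duration of Levosert usage is defined as the difference in time between removal (with or without replacement) and insertion of the device", and a denominator of all users. There is none: an expected duration properly runs over all users, and restricting it to devices already removed would shorten it artificially.

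It is also fair to say that national sales may not describe this sample. Respondents must have removed at least one device used for heavy menstrual bleeding and have at least four years as specialists (S5), so they may hold more of the older insertions.

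**Conclusion.** The point holds in a conditional form. Q7 leaves its denominator open and offers no opt-out, while by Table 2 roughly 68-72% of devices sold to 2020 had not reached six years by early 2023. Tally answers would be biased towards longer use and projected-risk answers would not, and the data collected cannot tell them apart.

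If every respondent tallied the whole caseload, the excess at the 7-year tail value would be about 0.2-0.4 years, or 0.4-0.65 years with 2021-22 sales set at the 2020 level. For that tail value this is an upper-end illustration and should not be quoted as the expected bias. It rests on assumed Year 6 retention of 20-55%, sales as a proxy for insertions, and fielding in early 2023. A larger tail answer would enlarge it. The study is descriptive and tests no hypothesis, so what is at stake is the meaning of the primary estimate, not an error rate. The change is cheap and can only be made before the survey is fielded.

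**What to change.** 1. In each row of Q7, tell the respondent to consider only patients in whom Levosert was inserted at least that many years ago, whether or not it has since been removed.
2. Add to each row an option for having no such patients or not enough experience.
3. Adapt the Q7 validation check. It now requires each row to be at least as large as the one before, which need not hold once the rows have different denominators. State in Section 10.1 how falling or missing rows enter the yearly likelihoods.
4. Report the six-year restricted mean next to the primary estimate. It does not use the 7-10 year tail answer, but it still rests on Q7, so it supplements items 1 to 3 and does not replace them.

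A condition per row is preferable to limiting all six rows to insertions at least six years old. That limit would discard sound Year 1 to 5 information from about 70% of devices and favour the earliest cohorts.

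Cost: rewording one item, adding one option per row, changing one programmed check, and ethics committee approval of the revised questionnaire in each country. Fewer respondents will contribute to the later rows, most of all in Serbia. Sales there to 2016 were 323 + 907 = 1,230 for 1,600 practising OB-GYNs, or about 0.8 each and 0.4 for heavy menstrual bleeding at 55%, against a quota of 100; eligible Prescribers will have more than this average. The questionnaire also takes slightly longer.
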